2.2.1 Subgroup of interest

No subgroup analysis is planned.

2.3 Participant disposition, demographics and other baseline characteristics

Safety analysis set will be used for the below analyses.

2.3.1 Participant disposition

Subject disposition will be summarized by treatment group and disposition event.

The number and percentage of subjects screened, randomized, completed, and discontinued from the study will be summarized with reasons of discontinuation.

2.3.2 Demographics and other baseline characteristics

Country-specific regulations should be considered for the collection of demographic and baseline characteristics in alignment with CRF.

Participant demographics: date or year of birth (if permitted), sex, race, predominant ethnicity (if permitted) and relevant medical history/current medical conditions (until date of signature of informed consent) will be recorded in the eCRF. Where possible, the diagnosis and not symptoms should be recorded. Participant race/ethnicity data are collected and analyzed to identify any differences in the safety and/or efficacy profile of the treatment due to these characteristics. In addition, we will assess the diversity of the study population as required by Health Authorities.

All prescription medications, over-the-counter drugs, and significant non-drug therapies prior to the start of the study must be documented. Details on concomitant therapy will be recorded on the appropriate page of the eCRF.

2.4 Treatments (study treatment, rescue medication, concomitant therapies, compliance)

The safety analysis set will be used for the analyses below.

2.4.1 Study treatment / compliance

Administration of drugs for each treatment group will be summarized as a frequency table of number of doses received.

Dose administration records will be listed by treatment group, CCI and participant.

2.4.2 Prior, concomitant and post therapies

Concomitant medications and significant non-drug therapies prior to and after the start of the study treatment will be listed and summarized according to the Anatomical Therapeutic Chemical (ATC) classification system, by treatment group and CCI as well as by ATC and treatment group.

2.5 Analysis supporting primary objective(s)

Commercially Confidential Information

All subjects within the safety analysis set will be included for the primary safety analyses.

The primary objectives of the study include assessing the efficacy of MBL949 in reducing weight and evaluating its safety and tolerability.

2.5.1 Primary endpoint(s)

Weight

The primary endpoint for efficacy is change-from-baseline in weight at week 16. Baseline weight is defined as the last weight measurement before dosing.

Adverse Events

Primary endpoints for safety and tolerability are occurrences and severities of adverse events.

2.5.2 Statistical hypothesis, model, and method of analysis

Weight

Commercially Confidential Information

Summary statistics will be provided by treatment, CCI and visit for weight and weight-change-from-baseline and also by treatment and visit CCI .
Graphs will also be produced by treatment, and visit for weight and weight-change-from-baseline. Additional graphs may be produced for weight. Frequency tables of responders, who

are participants with $\geq 5\%$ weight loss at a certain visit, will be provided by treatment, CCI and visit as well as by treatment and visit only.

2.5.3 Handling of intercurrent events

Commercially Confidential Information

2.5.4 Handling of missing values not related to intercurrent event

All participants with a baseline weight and at least one post-baseline weight measurement will be included in the primary efficacy analysis. Commercially Confidential Information

2.5.5 Sensitivity analyses

Commercially Confidential Information

2.5.6 Supplementary analyses

Commercially Confidential Information

2.6 Analysis supporting secondary objectives

N/A

2.7 Safety analyses

For all safety analyses, the safety analysis set will be used. All listings and tables will be presented by treatment group CCI .

2.7.1 Adverse events (AEs)

All information obtained on adverse events will be displayed by treatment group, CCI and participant.

The number (and percentage) of participants having treatment emergent adverse events (events started after the first dose of study medication or events present prior to start of treatment but increased in severity based on preferred term) will be summarized in the following ways:

- By treatment, primary system organ class and preferred term.
- By treatment, primary system organ class, preferred term, and maximum severity.
- By treatment, Standardized MedDRA Query (SMQ) and preferred term.

Separate summaries will be provided for study medication related adverse events, death, serious adverse events, and other significant adverse events leading to discontinuation.

A participant with multiple adverse events within a primary system organ class is only counted once towards the total of the primary system organ class.

2.7.1.1 Adverse events of special interest / grouping of AEs

N/A

2.7.2 Deaths

Deaths will be listed by treatment group, CCI and subject.

2.7.3 Laboratory data

All laboratory data will be listed by treatment group, CCI participant, and visit/time and if normal ranges are available, abnormal laboratory data will be flagged. Summary statistics of laboratory parameters will be provided by treatment group and visit/time. Urinalysis lab parameters will be further separated by gender.

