Visit Name	Screening	Baseline	Day 1	Day 2 ²	Day 5 ²	Day 7 ²	Day 10 ²	Day 15 / Week 2 ²	Day 29 / Week 4 ²	Day 43 / Week 6 ²	Day 57 / Week 8 ²	Day 71 / Week 10 ²	Day 85 / Week 12 ²	Day 99 / Week 14 ²	Day 100 ²	Day 103 ²	Day 105 ²	Day 108 ²	Day 112 / Week 16 ²	Day 140 / Week 20 ²	Day 169 / Week 24 / EOS ²
Visit Numbers ¹	1	20	100	110	120	130	140	150	160	170	180	190	200	210	220	230	240	250	260	270	1999
Days	-35 to -15	-14 to -1	1	2	5	7	10	15	29	43	57 ±1	71	85	99	100	103	105	108	112 ±1	140	169
Time (post-dose)	-	-	-	24h ±2	96h ±2	144h ±2	216h ±2	-	-	-	-	-	-	-	24h ±2	96h ±2	144 h ±2	216h ±2	312h ±2	984h ±6	1680 ±6

³ Final review of all eligibility criteria prior to dosing

⁴ As required per COVID-19 protocols at the site and local regulations

⁵ Complete Physical examination to be done. All other PEs will be abbreviated.

⁶ To be collected pre dose

⁷ Commercially Confidential Information

8

9

10

11

12

13

14

15

¹⁵ To be administered fasting, before lunch, before dinner, and before bedtime

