9.1 Discontinuation and completion

9.1.1 Study treatment discontinuation and study discontinuation

Discontinuation of study treatment for a participant occurs when study treatment is permanently stopped for any reason (prior to the planned completion of study drug administration, if any) and can be initiated by either the participant or the investigator.

The investigator must discontinue study treatment for a given participant if, he/she believes that continuation would negatively impact the participant's well-being.

Study treatment must be discontinued under the following circumstances:

- Participant/guardian decision
- Pregnancy
- Use of prohibited treatment as per recommendations in the prohibited treatment [Section 6.2.2](#)
- Any situation in which study participation might result in a safety risk to the participant
- If a liver or renal event occurs, follow guidelines outlined in [Section 16](#) regarding discontinuation of study treatment.
- Severe hypersensitivity reaction occurs, including any of the following: anaphylaxis, fever, chills, urticaria, dyspnea, headache, myalgia, hypotension
- Any laboratory abnormalities that in the judgment of the investigator, taking into consideration the participant's overall status, prevents the participant from continuing participation in the study
- Emergence of any medical or psychological issue in which in the PI assessment of the participant leads to the conclusion now has a risk of participating
- Following emergency unblinding

If discontinuation of study treatment occurs, the investigator should make a reasonable effort to understand the primary reason for the participant's premature discontinuation of study treatment and record this information.

Participants who discontinue study treatment or who decide they do not wish to participate in the study further should NOT be considered withdrawn from the study UNLESS they withdraw their consent (see 'Withdrawal of Informed Consent' [Section 9.2](#)). **Where possible, they should return for the assessments indicated** in the Assessment Schedule. If they fail to return for these assessments for unknown reasons, every effort (e.g. telephone, e-mail, and letter) should be made to contact the participant/pre-designated contact as specified in the lost to follow-up [Section 9.1.3](#). This contact should preferably be done according to the study visit schedule.

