- Dose not changed
- Dose increased/Dose reduced
- Drug interrupted/withdrawn

6. Its outcome (recovery status or whether it was fatal)

Conditions that were already present at the time of informed consent should be recorded in medical history of the participant.

Adverse events (including lab abnormalities that constitute AEs) should be described using a diagnosis whenever possible, rather than individual underlying signs and symptoms.

Adverse event monitoring should be continued until the end of study visit.

Once an adverse event is detected, it must be followed until its resolution or until it is judged to be permanent (e.g., continuing at the end of the study), and assessment must be made at each visit (or more frequently, if necessary) of any changes in severity, the suspected relationship to the interventions required to treat it, and the outcome.

Information about adverse drug reactions for the investigational drug can be found in the Investigator's Brochure (IB).

Abnormal laboratory values or test results constitute adverse events only if they fulfill at least one of the following criteria:

- they induce clinical signs or symptoms
- they are considered clinically significant
- they require therapy

Clinically significant abnormal laboratory values or test results must be identified through a review of values outside of normal ranges/clinically notable ranges, significant changes from baseline or the previous visit, or values which are considered to be non-typical in participant with the underlying disease. Alert ranges for laboratory and other test abnormalities are included in [Section 16.1](#).

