16.3 Appendix 3: Specific Renal Alert Criteria and Actions and Event Follow-up

Table 16-4 Specific Renal Alert Criteria and Actions

Confirmed serum creatinine increase 25 – 49%	
 ● Consider causes and possible interventions ● Follow up within 2-5 days
Serum creatinine increase $\geq 50\%$ ⁺ OR if <18 years old, eGFR < 35 mL/min/1.73 m ²	
 ● Consider causes and possible interventions ● Repeat assessment within 24-48h if possible ● Consider drug interruption or discontinuation unless other causes are diagnosed and corrected ● Consider patient hospitalization and specialized treatment
New onset dipstick proteinuria $\geq 3+$ OR Protein-creatinine ratio (PCR) $\geq 1\text{g/g Cr}$ (or mg/mmol equivalent as converted by the measuring laboratory)	
 ● Consider causes and possible interventions ● Assess serum albumin & serum total protein ● Repeat assessment to confirm ● Consider drug interruption or discontinuation unless other causes are diagnosed and corrected
New onset hematuria $\geq 3+$ on urine dipstick	
Assess & document:
 
 ● Repeat assessment to confirm ● Distinguish hemoglobinuria from hematuria ● Urine sediment microscopy ● Assess sCr ● Exclude infection, trauma, bleeding from the distal urinary tract/bladder, menstruation ● Consider bleeding disorder

+ Corresponds to KDIGO criteria for Acute Kidney Injury

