16.3.1 Renal Event Follow-Up

Table 16-5 Renal Event Follow-Up

Assess, document and record in CRF:
 
• Urine dipstick and sediment microscopy evidence of DIN: crystals, red blood cells (dysmorphic/glomerular vs. non-dysmorphic/non-glomerular), white blood cells, tubular epithelial cells• Blood pressure and body weight• Serum creatinine, BUN, electrolytes (sodium, potassium, phosphate, calcium), bicarbonate and uric acid• Urine output

Review and record possible contributing factors to the renal event (co-medications, other co-morbid conditions) and additional diagnostic procedures (MRI etc.) in the CRF

Monitor patient regularly (frequency at investigator's discretion) until -
 
• Event resolution: (sCr within 10% of baseline or PCR < 1 g/g Cr, or ACR <300 mg/g Cr) or• Event stabilization: sCr level with $\pm 10\%$ variability over last 6 months or proteincreatinine ratio stabilization at a new level with $\pm 50\%$ variability over last 6 months.• Analysis of urine markers in samples collected over the course of the DIN event

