2.1.1 General definitions

Study treatment refers to MBL949 or placebo. Commercially Confidential Information

The term '*date of first administration of study drug/treatment*' refers to the date on which the study drug/treatment was given for the first time in the CMBL949A12201 study.

The term '*date of last administration of study drug/treatment*' refers to the date on which the study drug/treatment was given for the last time in the CMBL949A12201 study.

The term '*study day*' refers to the Analysis Relative Day, Relative Start Day, or Relative End Day, as applicable. Day 1 is defined as the date of first dose of study drug (MBL949 or placebo).

Study day is defined as the number of days since the date of first dose of study treatment (Day 1).

Therefore, for a particular date, study day will be calculated as follows:

- for dates on or after the first administration of study treatment,
Study day = Assessment date – Date of first dose of study treatment +1
- for dates prior to the date of first administration of study treatment,
Study day = Assessment date – Date of first dose of study treatment.

The term '**baseline**' refers to the last non-missing assessment prior to the first dose of study drug, unless specified otherwise.

The term '**Treatment period**' refers to the 14 weeks period from Day 1 to Day 99.

The term '**treatment-emergent adverse event**' refers to any adverse event (AE) started after the first dose of study medication, or events present prior to the start of treatment but increased in severity based on preferred term (PT).

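### In the readable SAP, a creatinine rise that meets the protocol's own ≥50% renal alert may go unflagged, and no laboratory table counts such rises by arm

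*SAP*

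**What the plan says.** **Laboratory reporting.** SAP 2.7.3 lists all laboratory data and continues: "if normal ranges are available, abnormal laboratory data will be flagged. Summary statistics of laboratory parameters will be provided by treatment group and visit/time". SAP 2.1 defines the summaries for continuous data as mean, SD, median, minimum and maximum. It also mentions shift tables and tables of abnormal values, but no readable text gives their criteria. SAP 5.3 is headed as laboratory derivations, yet it holds only blood-pressure and pulse limits. Protocol 12.4.3 has the same normal-range rule for laboratory data.

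**Renal alerts.** Protocol Table 16-4 (Appendix 3) has two creatinine tiers: a confirmed increase of 25–49%, and an increase of at least 50%. The footnote to the second reads "Corresponds to KDIGO criteria for Acute Kidney Injury". The table does not name the reference value. Table 16-5 points to baseline, because its resolution criterion begins "Event resolution: (sCr within 10% of baseline". In SAP 2.1.1, baseline "refers to the last non-missing assessment prior to the first dose of study drug, unless specified otherwise". For creatinine this is normally the Day 1 sample, which Table 8-1 footnote 6 marks "To be collected pre dose".

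**The investigator's route.** Protocol 10.1.1 has the investigator look for clinically significant results by reviewing, among other things, "significant changes from baseline or the previous visit". Protocol 9.1.1 says "If a liver or renal event occurs, follow guidelines outlined in" Section 16. Protocol 10.1.1 also says "Alert ranges for laboratory and other test abnormalities are included in" Section 16.1, and protocol 8.4.1 cites 16.1 for notable laboratory findings. The readable text of 16.1 gives vital-sign limits only. The liver and renal laboratory alerts are in 16.2 and 16.3.

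**The concern.** The protocol judges creatinine by relative change, while the readable SAP judges it by position against a fixed range. A participant who starts well below the upper limit can meet the protocol's acute kidney injury criterion and still have every value in range. That participant carries no flag. The by-visit summaries do not link a value to the participant's own baseline.

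The remaining by-arm count is in the AE tables. Under protocol 10.1.1 a laboratory value becomes an AE only if it causes signs or symptoms, is considered clinically significant, or needs therapy. So the readable plan has no by-arm count of these rises that is free of that judgement. Safety and tolerability are a primary objective, and protocol 6.6.2 describes this as the first repeat-dose study of MBL949 in this population.

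**Working it through.** The documents give no figure for this point, so there is nothing to reproduce. The check is arithmetic.

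**Inputs**
- Flag: value outside the normal range (SAP 2.7.3).
- Alert: rise of at least 50%, with a lower tier of 25–49% (Table 16-4).
- Arm size: 12 completers (protocol section 3). Scaling by planned randomisation gives 12 × 106/90 = 14.1, so about 14 randomised.
- Scheduled post-dose chemistry (Table 8-1): Days 10, 15, 29, 43, 57, 71, 85, 99, 112, 140 and 169, which is 11 visits.
- Assumption: creatinine ULN of 1.0 to 1.3 mg/dL. The documents do not give it.

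**Step 1. When a rise stays unflagged.** A baseline b that rises by fraction r reaches b(1+r). It stays in range if b(1+r) ≤ ULN, that is, if b ≤ ULN/(1+r).

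| Rise | Calculation | Highest unflagged baseline, % of ULN |
|---|---|---|
| 25% | 1/1.25 | 80.0 |
| 49% | 1/1.49 | 67.1 |
| 50% | 1/1.50 | 66.7 |
| 75% | 1/1.75 | 57.1 |
| 100% | 1/2.00 | 50.0 |

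The limit falls as the rise grows. From a baseline of 60% of ULN:
- a 50% rise reaches 0.60 × 1.50 = 90% of ULN and is not flagged;
- a 75% rise reaches 0.60 × 1.75 = 105% and is flagged;
- a doubling reaches 0.60 × 2.00 = 120% and is flagged.

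**Step 2. In mg/dL, under the assumed ULN.** For a 50% rise the limit is 1.0/1.5 = 0.67 to 1.3/1.5 = 0.87 mg/dL. For a doubling it is 1.0/2 = 0.50 to 1.3/2 = 0.65 mg/dL.

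**Step 3. What the by-visit summary shows.** One participant rising 50% to exactly ULN gains ULN/3, which is 0.333 to 0.433 mg/dL. The arm mean at that visit moves by 0.333/14 = 0.024 to 0.433/12 = 0.036 mg/dL. That participant's value does not take the visit maximum above ULN.

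**Step 4. What the listing holds.** At full attendance there are 106 × 11 = 1,166 scheduled post-dose creatinine values, or 12 × 11 = 132 to 14 × 11 = 154 per active arm. Finding a relative rise means comparing each value with that participant's baseline.

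**The case against.** **Table 16-4 guides participant management and sets no reporting rule.** This stands. No readable text promises to tabulate it. A reader might infer that the SAP departs from the protocol, but the documents do not support that, since protocol 12.4.3 has the same normal-range rule. Protocol 12.4.3 does plan ECG counts that include changes from baseline. That shows such counts were thought useful in this trial, but it can equally be read as a deliberate choice not to plan them for laboratory data.

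**The data are handled elsewhere.** Largely true. All values are listed, investigators review changes from baseline, and Table 16-5 sends renal-event creatinine and contributing factors to the CRF. Reported AEs are counted by preferred term, maximum severity and SMQ. Because the listing is by participant, each comparison is about 11 values against one baseline for 12 to 14 people per active arm. A reader might infer that a renal signal would be lost, and it would not be. What remains is that no readable laboratory output counts these rises by arm.

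**The rule may be in redacted text.** This cannot be excluded. SAP 5.6 (variable derivations) and the blocks after 2.7.4.2 are redacted, and the criteria for the shift tables are not readable. If those tables use the normal range, an in-range rise stays in the normal category.

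**The size shows no consequence.** It shows that the range flag and the by-visit summaries can miss such a rise. It does not show that such rises will occur, and the readable text identifies no renal risk for this drug.

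**Conclusion.** The point holds as a low-cost improvement to the safety reporting. In the readable SAP, a creatinine rise that meets the protocol's ≥50% alert may go unflagged, and no laboratory table counts such rises by arm.

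A reader might infer that every rise of 50% or more from a baseline at or below 66.7% of ULN escapes the flag. It does not. That limit is exact only for a rise of 50%; it falls to 50% of ULN for a doubling, and larger rises from higher baselines are flagged.

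The conclusion rests on three things:
- baseline as the reference, inferred from Table 16-5 because Table 16-4 names none;
- a constant ULN for each participant, which is reasonable because protocol 8.4.1 uses a central laboratory;
- the readable text alone.

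The percentage limits need no assumed ULN, but the mg/dL figures do.

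The wrong cross-reference to 16.1 is a separate and smaller point. It matters because 10.1.1 is where the investigator decides whether a laboratory change is an AE.

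**What to change.** 1. **SAP 5.3.** For each participant derive the maximum post-baseline serum creatinine rise, 100 × (value − baseline)/baseline, over all scheduled and unscheduled values. State that the reference is the SAP 2.1.1 baseline.
2. **SAP 2.7.3.** Add a descriptive table of the number and percentage of participants in each treatment group with a maximum rise of at least 50%, and a listing of those participants' creatinine values.
3. **Optional row.** A row for ≥25% to <50% may be added if it is labelled *any single value, not confirmed*. Table 16-4 asks for confirmation in that tier without giving a rule, so a single-value count does not measure that alert.
4. **Protocol 8.4.1 and 10.1.1.** Point the laboratory alert references to 16.2 and 16.3.

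The cost is two short SAP edits, one small table and one listing from chemistry data already collected, plus two corrected references. No clinical threshold changes. With 12 to 14 participants per active arm the counts will be small, and some single-value rises will be transient. If redacted SAP text already contains the count, only step 4 is needed.

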2.7.4 Other safety data

2.7.4.1 ECG and cardiac imaging data

PR, QRS, QT, QTcF, RR intervals and HR will be obtained from single 12-lead ECGs for each participant during the study.

Abnormal ECG will be flagged and listed by treatment group, participant, and visit/time.

The total number and percentage of subjects with abnormal ECGs will be summarized by treatment group and visit.

2.7.4.2 Vital signs

All vital signs data will be listed by treatment group, CCI participant, and visit/time and if ranges are available, abnormalities (and relevant orthostatic changes) will be flagged. Summary statistics will be provided by treatment, and visit/time.

Vital signs values outside normal range will be listed by treatment group, CCI and subject.

Commercially Confidential Information

Commercially Confidential Information

Commercially Confidential Information

Commercially Confidential Information

Commercially Confidential Information

